## **5.4. Exploratory Efficacy Variable(s)**

### **5.4.1. Definition**

The following exploratory efficacy endpoints at Week 12 will also be analyzed:

- the proportion of subjects with  $\geq 10\%$  weight loss from baseline

- the change from baseline in BMI
- the change from baseline in waist circumference
- the change from baseline in glycated hemoglobin (HbA1c)
- the change from baseline in fasting plasma glucose (FPG)
- the change from baseline in fasting insulin
- the change from baseline in fasting C-peptide
- the changes from baseline in Homeostasis Model Assessment for B cell function (HOMA-B) and HOMA-insulin resistance (IR)
- the change from baseline in SBP
- the change from baseline in DBP
- the change from baseline in pulse rate
- the change from baseline in rate pressure product
- the change from baseline in fasting lipids (total cholesterol, LDL-C, HDL-C, and triglycerides)
- the change from baseline in scores on the Impact of Weight on Quality of Life – Lite (IWQOL-Lite)
- the change from baseline in scores on the Patient-Reported Outcomes Measurement Information System (PROMIS®) Physical Function Short Form 10a (PROMIS SF 10a)
- the change from baseline in scores on the Eating-related Concept Questionnaire (ERCQ)

#### **5.4.2. Analysis Methods**

The analysis of exploratory endpoints will use the observed data through Week 12 while on treatment (up to the last dose of study drug plus 14 days). The analysis of glycemic parameters (e.g., HbA1c, FPG, fasting insulin, HOMA-B, HOMA-IR) will be based on the measurements prior to rescue medication. The continuous exploratory efficacy endpoints (i.e., change from baseline in BMI, HbA1c, FPG, HOMA-B, HOMA-IR, SBP, DBP, pulse rate, and rate pressure product) with more than one planned post-baseline timepoint will be analyzed using a MMRM model similar to the model used to analyze the primary efficacy endpoint based on the mITT analysis set. An analysis of covariance (ANCOVA) model with treatment as a fixed effect and baseline measurement as a covariate will be used for endpoints with only one planned post-baseline timepoint (e.g., waist circumference, fasting insulin, fasting C-peptide, total cholesterol, LDL-C, and HDL-C). Shift tables will be used to summarize obesity class (Class I = 30 kg/m^2 – 34.9 kg/m^2; Class II = 35 kg/m^2 – 39.9 kg/m^2; Class III = ≥ 40 kg/m^2) at baseline versus end of treatment.

The categorical exploratory efficacy endpoints will be analyzed using a logistic regression model similar to the model used to analyze the proportion of subjects with ≥5% weight loss.

An ANCOVA model with treatment as a fixed effect and baseline measurement as a covariate will be used to analyze the exploratory PRO endpoints. The additional PRO analyses will be described in a separate SAP.

## **6. SAFETY**

All safety analyses and summaries will be based on the safety analysis set (Section 2.2.3). Safety data will be analyzed according to the predominant treatment received, in the event that a subject received a treatment other than that to which they were randomly assigned to receive. The predominant treatment is defined as the treatment to which the subject was exposed for the greatest duration during the double-blind treatment phase.

The evaluation of safety will be based on the incidence of adverse events, hypoglycemia episodes, and changes in clinical laboratory test results and vital sign results (blood pressure and pulse rate). The safety analyses will be based on the safety analysis set including all data, regardless of the initiation of glycemic rescue therapy (ie, including data after initiation of rescue therapy). Additional analysis of hypoglycemia will be performed based on the data prior the initiation of glycemic rescue therapy only. There will be no imputation of missing values for clinical laboratory test results and vital sign measurements in the safety analyses and there will be no hypothesis testing for results from safety analyses. Summaries of AEs, clinical laboratory test results, and vital sign results will be provided by treatment group and for the combined JNJ-64565111 treatment group.

### **6.1. Adverse Events**

The verbatim terms used in the CRF by investigators to identify adverse events will be coded using the Medical Dictionary for Regulatory Activities (MedDRA). A treatment-emergent AE (TEAE) is defined as an adverse event with an onset after the initiation study medication and before the last study medication date of the double-blind (12-week) treatment phase plus 35 days. AEs with a start date prior to initiation of double-blind study medication which are subsequently reported to have either an increase in intensity or change in attribution in relationship to study medication (i.e., no attribution to possible, probably, very likely) after the initiation of double-blind study medication will also be considered as TEAEs.

If the event occurs on the day of the initial administration of study agent, and either event time or time of administration are missing, then the event will be assumed to be treatment emergent. If the event date is recorded as partial or completely missing, then the event will be considered to be treatment emergent unless it is known to be prior to the first administration of study agent based on partial onset date or resolution date. All reported treatment-emergent adverse events will be included in the analysis. For each adverse event, the number and percentage of subjects who experience at least 1 occurrence of the given event will be provided by preferred term, grouped by system organ class (SOC), and presented by treatment group. In addition, comparisons between treatment groups may be provided as needed.

Summary tables will be provided for:

- AEs
- AEs leading to discontinuation
- Drug-related AEs
- Drug-related AEs leading to discontinuation
- Serious AEs (SAEs)
- Serious AEs leading to discontinuation
- Serious drug-related AEs leading to discontinuation and deaths
- AEs by system organ class
- AEs by severity
- AEs by relationship to study agent: related (which includes possibly related, probably related and very likely related, as reported by the investigator) and not related (which includes not related and doubtfully related, as reported by the investigator)
- AEs by the action taken regarding the study medication
- AEs by outcome

In addition to the summary tables, listings will be provided for subjects who had:

- SAEs
- AEs leading to discontinuation

Incidence of other treatment-emergent adverse events of special interest will be summarized.

Deaths will be displayed by actual treatment received. Frequencies for the following parameters will be included in the summary table:

- Number of subjects who died
- Cause of death
- Relationship to study agent (yes/no)

A listing of subjects who died will be provided.

As a screening tool, the 95% CIs for percentage difference between JNJ-64565111 and placebo will be provided for the AEs which are reported in at least four or more subjects in any treatment group during the treatment phase. Four (rule-of-4) is chosen based on the recommendation from the Safety, Planning, Evaluation, and Report (SPERT). No multiplicity adjustment will be applied. The exclusion of “0” in the 95% CI around the difference in incidence (JNJ-64565111 compared to placebo) for a particular AE does not necessarily imply that the higher incidence is related to drug. The intent of providing the 95% CIs is as a filter to identify AEs that require additional assessment.

Adverse events that are identified by the above screening procedure will be subject to further evaluation. The additional assessment may include some or all of the following, comparing JNJ-64565111 and placebo:

1. Investigator assessed relationship of AE to study drug, investigator assessed intensity of AE
2. Time to AE relative to start of double-blind study medication, duration of AE, action taken on study drug/occurrence of AEs leading to discontinuation
3. Other relevant safety information such as observations in other trials.

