Subjects who prematurely discontinue study drug will require an immediate EOT assessment (either on the day of study drug discontinuation or as soon as possible following study drug discontinuation) and the SAE follow-up visit. Subjects that discontinue study drug early will continue in the study and be assessed with the off-treatment procedures at the subsequent visit(s) per the Schedule of Activities table, starting at the next scheduled visit from when study drug was permanently discontinued up to the final Week 12 visit. These off-treatment visits will include collection of SAEs, specific AEs of interest (ie, major adverse cardiac events [MACEs], acute pancreatitis, and possible cases of thyroid neoplasm), vital signs (including body weight), and concomitant medications. All subjects, except those who died, were lost to follow-up, or have a withdrawn consent, will have a follow-up visit at least 5 weeks after the last dose of study drug was taken to collect any SAEs and blood samples for PK and immunogenicity ADA assessments will be obtained.

The ERCQ is a home-based assessment in contrast to the IWQOL-Lite, PROMIS SF 10a, Patient Global Impression Status (PGIS), and Patient Global Impression of Change (PGIC), which are site-based assessments.

Subjects who withdraw from the study will not be replaced.

During the 12-week treatment phase (Day 1 to Week 12), subjects meeting protocol-specified glycemic rescue criteria will have rescue therapy initiated, and will remain in the study, continuing double-blind study drug. Rescue therapy may include increasing the dose of a current AHA or the initiation of a new AHA. Investigators will manage rescue therapy, including the selection of the specific AHA, its clinically appropriate initial dose and titration regimen (if applicable), the need to switch from one AHA rescue medication to another (ie, poor glycemic response to prior rescue medication), and be consistent with the labeled use within the country of the study site. Metformin, sulphonylureas, thiazolidinediones (TZDs), sodium-glucose cotransporter 2 (SGLT-2) inhibitors, dipeptidyl peptidase-4 (DPP-4) inhibitors, and insulin (basal only) are allowed as rescue medication; GLP-1 agonists and short-acting or intermediate insulins are not allowed as rescue medication.

The overall study duration is approximately 19 weeks and comprises of 3 phases:

- Pretreatment phase: 3 weeks comprised of:
 - Screening phase: 1 week

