4.2.1. Study-Specific Ethical Design Considerations

This Phase 2b dose-ranging study is being conducted to assess the safety and efficacy of JNJ-64565111 over a 12-week period in severely obese subjects with T2DM and to provide information to select JNJ-64565111 dose(s) to be assessed in Phase 3 studies.

The primary ethical concern of this study is that the safety profile of JNJ-64565111 is not fully established and therefore subjects may be placing themselves at an increased risk of unexpected events by participating in this study. Although definitive information from studies in humans is not yet available, safety information from the Phase 1 studies indicates that JNJ-64565111 is generally well tolerated and no safety concerns precluding further clinical development have been identified. As discussed in Section 2.3, Benefit/Risk Assessment, clinical and laboratory evaluations will be performed throughout the study (according to the Schedule of Activities) to monitor the safety of subjects. Potential risks will be managed and minimized by appropriate protocol eligibility criteria, subject management procedures, specific discontinuation criteria, and careful internal safety monitoring.

Subjects who discontinue early from the study will have a post-study visit, so as to collect information on SAEs, and support a complete assessment of key safety events in the intact randomized study population. Specific monitoring algorithms are provided in case of elevations that warrant further follow-up and investigations in subjects experiencing prespecified elevation of these parameters.

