- Initiation and planned continued use of disallowed therapy (see Section [6.5](#), Prestudy and Concomitant Therapy)
- Subject is on glycemic rescue therapy, and after at least 2 weeks on the maximum dose considered appropriate by the investigator, FPG is >180 mg/dL (10.0 mmol/L)

- Subject experiences a SAE of biochemically-confirmed (eg, blood pH, serum β -hydroxybutyrate, anion gap) DKA
- Subject experiences an episode of vomiting assessed as “severe” lasting more than 24 hours and considered to be at least possibly related to study drug without any other potential cause (eg, viral gastroenteritis, food-borne illness).

Subjects who prematurely discontinue study drug prior to Week 12 will require an immediate EOT assessment (either on the day of study drug discontinuation or as soon as possible following study drug discontinuation) and the SAE assessment/follow-up and PK and immunogenicity (ie, ADA) collection at least 5 weeks since the last dose of study drug.

Subjects that discontinue study drug early will continue in the study (off treatment) and will be assessed at the subsequent visit(s) as described in the Schedule of Activities schedule, starting at the next scheduled visit from when study drug was permanently discontinued up to the final Week 12 visit. These off-treatment visits will include assessment and collection of:

- SAEs
- Specific AEs of interest (ie, MACE events, acute pancreatitis, and possible cases of thyroid neoplasm)
- Vital signs (including body weight)
- Concomitant medications

If subjects that discontinued study drug early are unable to return to their site for the scheduled on-site study visit, an alternate contact visit should be conducted with the goal of collecting any SAEs, MACEs (ie, CV death, nonfatal MI and nonfatal stroke), acute pancreatitis, and AEs of thyroid neoplasm. Details regarding discussions via telephone, email, or other methods of contact should be properly documented on subject’s source record and/or eCRF, including date of contact, outcome and responses provided by the subjects. The site may consult subjects’ delegated contact(s) for the off-treatment follow-up if the site is unable to reach the subjects after multiple attempts.

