9.4.2. Safety Analyses

The evaluation of safety will be based on the incidence of adverse events and hypoglycemia episodes, and changes in clinical laboratory test results and vital sign results (blood pressure, pulse rate). The safety analyses will be based on the safety analysis set including all data, regardless of the initiation of glycemic rescue therapy (ie, including data after initiation of rescue therapy). Additional analysis of hypoglycemia will be performed based on the data prior the initiation of glycemic rescue therapy only. Summaries of adverse events, clinical laboratory test results, and vital sign results will be provided by treatment group. There will be no imputation of missing values for clinical safety laboratory test results, and vital sign measurements.

Adverse Events

The verbatim terms used in the eCRF by investigators to identify adverse events will be coded using the Medical Dictionary for Regulatory Activities (MedDRA). Treatment-emergent adverse events are adverse events with onset during the treatment phase or that are a consequence of a pre-existing condition that has worsened since baseline. All reported adverse events will be included in the analysis. For each adverse event, the percentage of subjects who experience at least 1 occurrence of the given event will be summarized by treatment group. In addition, comparisons between treatment groups will be provided if appropriate.

Summaries, listings, datasets, or subject narratives may be provided, as appropriate, for those subjects who die, who discontinue study drug due to an adverse event, or who experience a severe or a serious adverse event.

For each adverse event, the percentage of subjects who experience at least 1 occurrence of the given event will be summarized by treatment group. The percentage of subjects with specific treatment-emergent adverse events (TEAEs) will be summarized by severity and relationship to study drug, as classified by the investigator, by treatment group. The dose-response relationship of dose levels on TEAE will be assessed, assuming that the incidence rates of TEAE will be monotonic with respect to dose levels. A listing for non-TEAEs will be provided.

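### Early stoppers are followed to Week 12 for serious and key events, but the SAP's adverse event analysis closes 35 days after the last dose, leaving up to 49 days outside the by-arm summaries

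*SAP*

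**What the plan says.** Protocol 7.1 (also 4.1 and footnotes b and c of the Schedule of Activities) keeps subjects who stop drug early in the study, off treatment, with visits "from when study drug was permanently discontinued up to the final Week 12 visit". Two kinds of safety event are sought at those visits: SAEs, and a second item that reads "Specific AEs of interest (ie, MACE events, acute pancreatitis, and possible cases of thyroid neoplasm". If a subject cannot attend, the site is to seek the same events by another form of contact.

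SAP 6.1 defines a treatment-emergent event by onset after the start of study medication and "before the last study medication date of the double-blind (12-week) treatment phase plus 35 days". It then states the scope: "All reported treatment-emergent adverse events will be included in the analysis". Its line on other events of special interest is also limited to treatment-emergent ones.

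Protocol 9.4.2 is wider. It puts every reported adverse event into the analysis and adds: "A listing for non-TEAEs will be provided". SAP 6.1 contains neither statement.

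For laboratory tests (SAP 6.2) and vital signs (SAP 6.3), the SAP plans two summaries: one restricted to 14 days after dosing, and one using all measurements whatever the time since last dose in subjects who stop before Week 12.

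**The concern.** The plan asks sites to go on looking for a short list of important events until Week 12, then applies a counting rule that ends earlier for anyone who stops in roughly the first half of treatment. Events found after that rule closes would not enter the by-arm incidence summaries. Safety and tolerability is one of the two primary objectives, and the SAP already avoids this loss for laboratory and vital-sign data. For serious events and events of interest it plans no equivalent.

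The data would be collected, but no by-arm count over the full 12 weeks would be made from them, except for deaths.

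**Working it through.** **Inputs**
- Week 12 target: Day 85 (SAP Table 2.1.1, Day 1 = first dose). Check: 12 × 7 + 1 = 85.
- Dosing: once weekly from Day 1 (Protocol 6.1), so planned doses fall on Days 1, 8, 15, … 78.
- Treatment-emergent cut-off: day of last dose + 35 (SAP 6.1).

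**Formula**

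Follow-up outside the window = max(0, 85 − (day of last dose + 35)).

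| Last dose (day) | Window closes (day) | Days to Day 85 not counted |
|---|---|---|
| 1 | 36 | 49 |
| 8 | 43 | 42 |
| 15 | 50 | 35 |
| 22 | 57 | 28 |
| 29 | 64 | 21 |
| 36 | 71 | 14 |
| 43 | 78 | 7 |
| 50 or later | 85 or later | 0 |

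**Sensitivity of the maximum (last dose Day 1)**
- Counting Days 36 to 85 inclusively, because onset must be before the cut-off: 50 days.
- Week 12 visit 4 days late (Day 89): 89 − 36 = 53 days.
- Week 12 visit at the end of the SAP window (Day 105): 105 − 36 = 69 days.

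So 49 days is the single-dose extreme at the nominal visit day.

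**Scale, on assumption only.** The documents give no rate or timing of early stopping. Suppose 10% to 30% of the 141 active subjects (3 × 47) stopped after one to four doses, evenly spread. The mean loss is (49 + 42 + 35 + 28)/4 = 38.5 days.
- 10%: 14.1 × 38.5 = 543 days, about 1.5 person-years.
- 30%: 42.3 × 38.5 = 1,629 days, about 4.5 person-years.
- Total active follow-up to Week 12: 141 × 84 = 11,844 days, about 32.4 person-years. The share left out is about 5% to 14%.

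This illustrates order of size only. It has no placebo counterpart, so it says nothing about imbalance between arms.

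**Where a late event could still appear**
- Deaths table (SAP 6.1): by actual treatment with no stated window, so a late cardiovascular death would be counted by arm.
- SAE listing (SAP 6.1): a late serious event could appear, but a listing is not a comparison.
- A non-serious event of interest, such as a thyroid nodule, has neither route.
- Events with missing or partial onset dates count as treatment-emergent unless known to precede the first dose.

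**The case against.** The 35-day window is a conventional choice with support in the documents. Footnote y of the Schedule of Activities monitors adverse events until 5 weeks after the last dose, and the follow-up visit falls then. With a half-life of 6 to 8 days (Protocol 4.3), 35 days is 35/8 = 4.4 to 35/6 = 5.8 half-lives, so roughly 2% to 5% of drug remains. That justifies the window for the main tables. It does not answer why the named events are sought to Week 12 and then left out of any by-arm summary.

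The SAP's exclusion is also not fully explicit. The bullets naming the summary tables do not repeat the treatment-emergent restriction, and the separate paragraph on events of interest states no window. The restriction comes from the scope sentence and the line on other events of special interest. If a wider scope is intended for SAEs, the SAP should say so.

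Four stronger readings are tempting and not supported:
- **That the off-treatment visits exist for a comparison in all randomized subjects.** Protocol 4.2.1 does speak of a visit to "support a complete assessment of key safety events in the intact randomized study population", but that aim is attached to the post-study visit for subjects who leave the study. The off-treatment visits also collect body weight, which feeds the retrieved-dropout imputation.
- **That the rule biases the comparison between doses.** Protocol 4.3 reports poorer tolerability above 10 mg, and no arm here exceeds 10 mg. Unequal loss by arm is possible but undocumented.
- **That late events disappear altogether.** The deaths table and the SAE listing remain.
- **That the SAP has cancelled the listing of non-treatment-emergent events.** SAP section 1 leaves output titles and mock-ups to a separate Data Presentation Specifications document, which is not available here, and the SAP amendment history records no such removal.

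**Conclusion.** The point holds as a minor gap in the analysis plan. As written, SAP 6.1 leaves 7 to 49 days of follow-up to the nominal Day 85 outside the by-arm adverse event and event-of-interest summaries for subjects whose last planned dose falls on Days 1 to 43. This is narrower than Protocol 9.4.2 and out of line with SAP 6.2 and 6.3.

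The conclusion rests on reading the SAP's scope sentence as governing the summary tables, and on weekly dosing with the Week 12 visit on its target day. The number of subjects affected and any difference between arms cannot be derived from the documents. Few such events should be expected, so the gain is completeness on a primary objective. No error in the main safety tables is shown.

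**What to change.** Keep the treatment-emergent tables as they are. Add to SAP 6.1 one supplementary table by treatment group, on the safety analysis set, of SAEs, deaths, MACE, acute pancreatitis and thyroid neoplasm, from first dose to the Week 12 visit (nominal Day 85) for all subjects, regardless of time since last dose. Limit it to these types, because other adverse events are not among those listed for collection at off-treatment visits.

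Use the same cut-off for everyone. Letting the table run on to the 5-week follow-up would give a completer with a last dose on Day 78 a horizon of 78 + 35 = Day 113, against Day 85 for a one-dose stopper. Completers' events after Day 85 stay in the treatment-emergent tables.

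Confirm that the listing of non-treatment-emergent events promised in Protocol 9.4.2 is among the planned outputs.

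The cost is the programming of one table from data already collected. A footnote should say that off-treatment ascertainment may be less complete where contact was remote or through a delegate, as Protocol 7.1 allows.
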